7.1.7. Withdrawal Due to an Adverse Event

Any patient who will experience an adverse event may be withdrawn from the study at any time at the discretion of the investigator. If a patient is withdrawn wholly or in part because of an adverse event, both the adverse events page and the termination page of the CRF will be completed at that time.

The patient will be monitored at the discretion of the investigator (eg, until the event has resolved or stabilized, until the patient is referred to the care of a healthcare professional, or until a determination of a cause unrelated to the study drug or study procedure is made). The investigator must inform the medical monitor as soon as possible of all patients who are being considered for withdrawal due to adverse events. Additional reports must be provided when requested.

If a patient is withdrawn from the study for multiple reasons that include adverse events, the termination page of the CRF should indicate that the withdrawal was related to an adverse event. An exception to this requirement will be the occurrence of an adverse event that, in the opinion of the investigator, is not severe enough to warrant discontinuation but requires the use of a prohibited medication, thereby requiring discontinuation of the patient. In such a case, the reason for discontinuation would be the need to take a prohibited medication, not the adverse event.

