4.3. Withdrawal Criteria and Procedures for the Patient

In accordance with the Declaration of Helsinki (in accordance with the applicable country's acceptance), patients may voluntarily withdraw from the study at any time. The investigator also has the right to withdraw a patient from the study in the event of intercurrent illness, adverse events, pregnancy (Section 7.2), or other reasons concerning the health or well-being of the patient or in the event of lack of cooperation.

Each patient is free to withdraw from the study at any time, without prejudice to his/her continued care. A patient must be withdrawn from the study if any of the following events occur:

1. Patient withdraws consent or requests discontinuation from the study for any reason.
2. Patient develops an illness that would interfere with his/her continued participation.
3. Patient is noncompliant with the study procedures and assessments or administration of IMPs in the opinion of the investigator.
4. Patient takes prohibited concomitant medications as defined in this protocol.
5. A female patient has a confirmation of pregnancy during the study from a positive pregnancy test.
6. The sponsor requests withdrawal of the patient.
7. Patient experiences an adverse event or other medical condition, which indicates to the investigator that continued participation is not in the best interest of the patient.

Should a patient decide to withdraw from the study after administration of study drug or should the investigator decide to withdraw the patient, all efforts will be made to complete and report all observations up to the time of withdrawal. A complete final evaluation at the time of the patient's withdrawal should be made, and an explanation should be given as to why the patient is withdrawing or being withdrawn from the study.

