5.6. Prior and Concomitant Medication or Therapy

Any prior or concomitant therapy, medication (including corticosteroids), or procedure a patient has had at screening up to the end of the study period, including follow-up, will be recorded on the appropriate CRF. Generic or trade name, indication, and dosage will be recorded. The sponsor will encode all therapy and medication according to the World Health Organization (WHO) drug dictionary.

At each clinic visit after the screening visit, the investigator will ask patients whether they have taken any medications (other than study drug), including over-the-counter medications, vitamins, or herbal or nutritional supplements, since the previous visit. Indication, dosage, and start and end dates should be entered on the appropriate CRF.

For patients on maintenance OCS treatment, patients should be evaluated at each patient interaction (study visit) and their OCS dose reduced as clinically appropriate. Maintenance prednisone will not be provided by the sponsor. In an effort to standardize a patient's maintenance therapy, it is encouraged that the investigators prescribe prednisone/prednisolone as the maintenance corticosteroid preparation if deemed necessary.

With the exception maintenance OCSs for the treatment of asthma, any systemic immunosuppressive or immunomodulatory biologic (eg, anti-immunoglobulin E mAb or other mAb [eg, mepolizumab, benralizumab, dupilumab] or soluble receptors) or non-biologic (eg, methotrexate or cyclosporine) will be prohibited during this study.

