### 5.2. Patient Disposition

Data from patients enrolled, patients enrolled but not treated, patients in the safety analysis set, patients who completed the treatment, patients who completed the study, patients who discontinued from treatment, and patients who withdrew from the study will be summarized using descriptive statistics. Data from patients who discontinue from the treatment and patients who withdrew from the study will also be summarized by reason for withdrawal. The previous study from which patients enrolled (30025 or 30027) will also be summarized, along with whether the patient was a seamless rollover or non-seamless rollover. This summary will include all patients enrolled into this study. The denominator for calculating the percentages will be the number of enrolled patients as appropriate.

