### 8.3. Adverse Events

Adverse events will be coded using the Medical Dictionary for Regulatory Activities (MedDRA); the final version number will be indicated in the summary tables.

On-treatment adverse event summaries will be presented by previous double-blind treatment group and for all patients, based on events with onset during the treatment period. If the AE start date is missing or partial, the event will be considered on-treatment unless there is evidence to the contrary (eg, month and year of AE start is present and is less than the month and year of the first dose of study drug). Post-treatment adverse events with onset during the follow-up period (ie, AE start date greater than the upper bound of the treatment period, as described in Section 4.4 previously) will be summarized separately.

Summaries will be presented by SOC and/or PT for all adverse events (overall and by severity), adverse events determined by the investigator to be related to study treatment (overall and by severity), serious adverse events, adverse events causing discontinuation from study treatment, and non-serious adverse events. Treatment related adverse event summaries will include events with missing relationship to study drug. For summaries by severity, patients will be counted at the greatest reported severity. Adverse events missing the flag indicating a serious adverse event will be excluded from the summary of serious adverse events, but included in the summary of non-serious adverse events.

In addition, adverse events that begin within 24 hours after study drug injection and injection-site adverse events (as recorded on the CRF) will each be summarized separately.

A summary for the most common adverse events (incidence  $\geq 2\%$  for all patients) will also be presented. Adverse events will additionally be presented for subgroups defined in Section 3.3.

All adverse events, including events with onset prior to the first dose of reslizumab in this study, will be included in the patient listings. The mapping of MedDRA dictionary terms for adverse event descriptions will also be provided.

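### The Protocol 7.1.7 exception can understate AE-related withdrawals: an AE not itself warranting discontinuation but needing a prohibited medication is recorded as a withdrawal for the medication

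*Protocol*

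**What the plan says.** **The recording rule.** Protocol 7.1.7 gives a general instruction and an exception in one paragraph. Where a patient leaves for several reasons and one is an AE, "the termination page of the CRF should indicate that the withdrawal was related to an adverse event". The exception covers an AE that, in the investigator's opinion, "is not severe enough to warrant discontinuation but requires the use of a prohibited medication", so that the patient has to stop. For that patient, "In such a case, the reason for discontinuation would be the need to take a prohibited medication, not the adverse event".

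**What makes a medication prohibited.** Protocol 5.6 bars systemic immunosuppressive or immunomodulatory treatment, whether biologic "or non-biologic (eg, methotrexate or cyclosporine) will be prohibited during this study", apart from maintenance oral corticosteroids for asthma. Protocol 4.3 puts this event on its list of reasons for compulsory withdrawal: "Patient takes prohibited concomitant medications as defined in this protocol".

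**Where the recorded reason is used.**
- SAP 5.2: "Data from patients who discontinue from the treatment and patients who withdrew from the study will also be summarized by reason for withdrawal". Protocol 9.4.1 plans the same for study withdrawals.
- SAP 8.3 plans a summary of "adverse events causing discontinuation from study treatment". Protocol 9.6 plans summaries and listings of AEs that lead to withdrawal.
- The tolerability paragraph of the Protocol synopsis relies partly on patient disposition.

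**The concern.** In the excepted case the AE creates the need for the drug, and the drug triggers the withdrawal. Without the AE the patient would have stayed. The general instruction would count this patient as AE-related; the exception takes the patient out of that category. No rule works in the opposite direction, so any error lowers the AE count.

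The study's primary objective is long-term safety, and withdrawals due to AEs are a planned safety output. There is no control arm, blinding or data monitoring committee. The exception turns on one investigator's opinion of whether the AE warranted stopping, and that threshold is not tied to the mild, moderate and severe scale in Protocol 7.1.3. An AE that needs an immunosuppressive or immunomodulatory agent is also one that a safety reader of an anti-IL-5 antibody would want to see linked to the withdrawal.

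**Working it through.** The plan states no figure for this point: no expected AE-withdrawal rate and no expected number of excepted cases. The check is therefore mainly a reading of the rule against the outputs that use it.

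**Step 1. Sort the possible withdrawals under Protocol 7.1.7.**
- A: the AE warrants stopping and no prohibited drug is needed. Recorded as AE.
- B: the AE warrants stopping and a prohibited drug is also needed. The exception does not apply, so the general instruction holds. Recorded as AE.
- C: the AE is judged not to warrant stopping but needs a prohibited drug, and the patient is withdrawn. Recorded as prohibited medication.
- D: a prohibited drug is taken for a reason unrelated to an AE. Recorded as prohibited medication.

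Only C is misattributed. C and D share one category, so a reader of the table cannot tell them apart.

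**Step 2. Follow case C into the outputs.**
- Disposition by reason (SAP 5.2): built on the recorded reason, so C is missing from the AE row. The total number of withdrawals does not change.
- AE-discontinuation summaries (Protocol 9.6, SAP 8.3): the source is not stated. Protocol 7.1.2 has the action taken with study drug recorded for each AE, separately from the termination page. If the table uses the termination page, C drops out here too. If it uses the per-event field, C may be counted, and the AE table and the disposition table can then disagree.
- Primary endpoint: Protocol 7.1.2 requires every AE in the study period to be recorded, whatever the reason for withdrawal. C has no effect on it.

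**Step 3. Scale.** Input: about 360 patients (Protocol 9.1, SAP 2.4). Assumption: all 360 are in the denominator. With m cases of type C, the AE-withdrawal percentage falls by 100 × m/360 points:
- m = 0: 0
- m = 1: 0.28
- m = 2: 0.56
- m = 5: 1.39
- m = 10: 2.78

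The values of m show the range only; the documents support no particular one. SAP 5.1 also presents these tables by previous double-blind treatment group. There the denominators are smaller and each case weighs more, but the split is not given.

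**The case against.** The strongest reply is that the exception is narrow and that little information is lost. Most of this stands.

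- **Narrow.** It applies only when the AE is judged not to warrant stopping. Few AEs need an agent from the 5.6 class and still meet that condition. A reader might infer that serious immune-mediated or malignant events are being hidden. The text does not support that: such an event would normally warrant stopping in its own right and stay coded as an AE.
- **Withdrawal may not follow.** Protocol 4.3 makes it compulsory, but Appendix C counts prohibited medication among possible protocol violations and lets the sponsor decide whether the patient continues. Protocol 7.1.9 allows case-by-case deviations after an AE. These passages need to be reconciled with 4.3. If a patient continues, there is no withdrawal to misattribute.
- **Steroid courses.** Because 5.6 excepts only maintenance oral corticosteroids, a reader might infer that any systemic steroid course, for instance for a hypersensitivity event, triggers the exception. The exacerbation definition in Protocol 6.1.1 includes systemic steroid use and handles repeat courses as a matter of analysis. That does not fit a reading under which each course forces withdrawal. The point does not rest on it.
- **Signal retained.** The AEs stay in the overall, severity and seriousness summaries. Hypersensitivity, malignancy, helminth infection and opportunistic infection have their own tables (SAP 8.3.1). Protocol violations and concomitant medications are summarized too.

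What the reply does not remove is the one-way rule for the disposition table and the unnamed source of the AE-discontinuation tables.

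**Conclusion.** The point holds in a limited form. The exception departs from the general instruction beside it and can lower the AE row of the disposition-by-reason table. It can also lower the AE-discontinuation summaries, but only if those are driven by the termination page, which neither document says.

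The number of affected patients is unknown, probably small and possibly zero. Each moves the rate by about 0.28 percentage points, assuming a denominator of 360. A reader might infer that the AE-withdrawal counts are in fact too low, or by a definite fraction. The documents do not support either: understatement needs at least one case of type C, and with no stated withdrawal rate there is no base for a relative figure. The effect is confined to the attribution of withdrawals; the primary endpoint is untouched and the study plans no inference.

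It is still more than a missing detail, because a written rule sends these cases in one direction in a study whose purpose is safety.

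**What to change.** The changes concern recording and counting only. They do not alter who is treated or withdrawn.

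1. Termination page: whenever an AE led to the prohibited medication, also record the AE as a contributing reason, and align Protocol 7.1.7 with this.
2. SAP 5.2 and 8.3: name the CRF field that defines an AE causing discontinuation.
3. SAP 5.2 and 8.3: count AE-prompted prohibited-medication withdrawals in the AE-discontinuation table, or show them as a separate, identified row.

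The cost is one protocol sentence, one CRF completion instruction and a line in the SAP. The SAP's Introduction gives it precedence where the two documents differ, so items 2 and 3 can be settled there even without a protocol amendment, and the change can be listed in SAP Section 14. Without item 1, the cases would have to be identified from the AE and concomitant-medication records. The downside is that the reported AE-withdrawal rate may be slightly higher.

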7.1.8. Overdose of Study Drug

Any dose of study drug, whether taken intentionally or unintentionally, in excess of that prescribed must be immediately reported to the sponsor. Medication errors will be captured as protocol violations or deviations depending on the error.

7.1.9. Protocol Deviations Because of an Adverse Event

If a patient experiences an adverse event or medical emergency, deviations from the protocol may be allowed on a case-by-case basis. To ensure patient safety, after the event has stabilized or treatment has been administered (or both), the investigator or other physician in attendance must contact the physician identified in the Clinical Study Personnel Contact Information section of this protocol as soon as possible to discuss the situation. The investigator, in consultation with the sponsor, will decide whether the patient should continue to participate in the study.

7.2. Pregnancy

Administration of IMP will be discontinued for any female patient who becomes pregnant during the study.

All pregnancies of women participating in the study that occur during the study, or within at least 5 months after the last IMP injection, are to be reported immediately to the individual identified in the Clinical Study Personnel Contact Information section of this protocol, and the investigator must provide the sponsor (LSO/CRO) with the completed pregnancy form. The process for reporting a pregnancy is the same as that for reporting a serious adverse event but using the pregnancy form (Section 7.1.5.3).

All female patients who become pregnant will be monitored for the outcome of the pregnancy (including spontaneous, elective, or voluntary abortion). If the pregnancy continues to term, the outcome (health of the infant up to 8 weeks of age), including details of birth and presence or absence of any birth defect, congenital abnormalities, or maternal and newborn complications, will be reported to the sponsor. Any complication of pregnancy during the study and any complication of pregnancy that the investigator becomes aware of after withdrawal from the study will be reported as an adverse event or serious adverse event, as appropriate.

If the pregnancy in the woman participating in the study does not continue to term, one of the following actions will be taken:

- For a spontaneous abortion, report as a serious adverse event
- For an elective abortion due to developmental anomalies, report as a serious adverse event
- For an elective abortion not due to developmental anomalies, report on the pregnancy form; do not report as an adverse event

7.3. Medication Error and Special Situations Related to the Investigational Medicinal Products

Any administration of IMP that is not in accordance with the study protocol should be reported on the CRF either as a violation, if it meets the violation criteria specified in the protocol

([Appendix C](#)), or as a deviation in the patient's source documents, regardless of whether or not an adverse event occurs as a result. When meeting protocol violation criteria, all instances of incorrect IMP administration should be categorized on the CRF as "Noncompliance to investigational medicinal product (IMP)."

The following are types of medication errors and special situations:

1. Medication error: Any unintentional error in the prescribing, dispensing, or administration of a medicinal product while in the control of the healthcare professional, patient, or consumer.
2. Overdose: Administration of a quantity of a medicinal product given per administration or cumulatively, which is above the maximum recommended dose according to the authorized product information. Clinical judgment should always be applied. Any dose of IMP, whether taken intentionally or unintentionally, in excess of that prescribed must be immediately reported to the sponsor.
3. Misuse: Situations where the IMP is intentionally and inappropriately used (not in accordance with the authorized product information).
4. Abuse: Persistent or sporadic, intentional excessive use of IMP that is accompanied by harmful physical or psychological effects.
5. Off-label use: Situations where an IMP is intentionally used for a medical purpose not in accordance with the authorized product information.
6. Occupational exposure: Exposure to an IMP, as a result of one's professional or nonprofessional occupation.
7. Breastfeeding: Suspected adverse reactions that occur in infants after exposure to a medicinal product from breast milk.

7.4. Clinical Laboratory Tests

All clinical laboratory test results outside of the reference range will be judged by the investigator as belonging to one of the following categories:

- abnormal and not clinically significant
- abnormal and clinically significant

A laboratory test result that is judged by the investigator as clinically significant will be recorded both on the source documentation and on the CRF as an adverse event and will be monitored as described in Section [7.1.2](#). An event may include a laboratory or diagnostic test abnormality (once confirmed by repeated testing) that results in the withdrawal of the patient from the study, the temporary or permanent withdrawal of IMP or medical treatment, or further diagnostic workup. (Note: Abnormal laboratory or diagnostic test results at the screening visit that preclude a patient from entering the study or receiving IMP are not considered adverse events.)

In addition, potentially clinically significant values will be predefined by the sponsor for selected laboratory parameters and will be detailed in the statistical analysis plan.

7.4.1. Serum Chemistry and Hematology

Clinical laboratory tests (serum chemistry and hematology) will be performed before IMP administration at the time points detailed in [Table 1](#). Clinical laboratory tests will be performed using the central laboratory. Specific laboratory tests to be performed are provided below and in [Appendix H](#).

7.4.1.1. Serum Chemistry

The following serum chemistry tests will be performed:

- calcium
- phosphorus
- sodium
- potassium
- chloride
- CPK (at scheduled visits as noted in [Table 1](#))
- bicarbonate or carbon dioxide
- glucose
- BUN
- creatinine
- ALT
- AST
- ALP
- total protein
- albumin
- total bilirubin
- direct bilirubin
- indirect bilirubin
- follicle stimulating hormone (FSH) level, as required

7.4.1.2. Hematology

The following hematology tests will be performed:

- hemoglobin
- hematocrit
- platelet count
- absolute neutrophil count

- WBC count and differential count
 - polymorphonuclear leukocytes (neutrophils)
 - lymphocytes
 - eosinophils (absolute values)
 - monocytes
 - basophils

7.4.2. Other Clinical Laboratory Tests

There will be no other clinical laboratory tests.

7.4.2.1. Human Chorionic Gonadotropin Tests

Human chorionic gonadotropin tests in serum will be performed for all women who did not seamlessly rollover to the OL extension. This will be performed at screening visit 0. Urine pregnancy tests will be performed at baseline, before study drug injection at each administration visit, at EOT or early withdrawal, and at home for the follow-up telephone assessment. Administration of IMP will be discontinued for any female patient who becomes pregnant during the study. Procedures for reporting the pregnancy are provided in Section 7.2.

7.5. Electrocardiography

A 12-lead ECG will be conducted at screening (visit 0), visit 1, and EOT or early withdrawal visit. ECGs should be obtained before other assessments (eg, blood draw and pulmonary function testing) and study drug administration. Standard ECG parameters will be recorded using the site's equipment, and the ECG will be interpreted locally by the Principal Investigator (or qualified physician) as normal or abnormal. If the ECG is read as abnormal, the Principal Investigator will indicate whether or not the abnormality is clinically significant (yes or no) and write in the detailed interpretation/diagnosis. Clinically significant abnormal ECG findings at baseline and screening should be recorded as part of the medical history. Any ECG finding that is judged by the investigator as a clinically significant change compared with a baseline value will be considered an adverse event, recorded on the source documentation and transcribed onto the CRF, and monitored as described in Section 7.1.2.

In addition, potentially clinically significant values will be predefined by the sponsor for selected ECG parameters and will be detailed in the statistical analysis plan.

